5.5.3 HeartEF Analysis

For each exam, the biplane left ventricular end-systolic volume, end-diastolic volume, and ejection fraction calculated from the HeartEF algorithm will be compared respectively to the average of the end-systolic volumes, end-diastolic volumes, and ejection fractions assessed by at least 3 different cardiologists on the novices' exams and experts' exams from the FAS population.

- The number and proportion of novices' and experts' exams on which HeartEF was able to make the quantitative assessment.
- The mean and standard deviation of the distribution of the left ventricle measurements on novices' and experts' exams.
- The mean, standard deviation, and 95% CI of the difference between the left ventricle assessment with HeartEF and the average of the assessments made by at least 3 cardiologists will be calculated.
- The concordance of the measurements will be assessed using the ICC and its 95% CI.
- The Pearson or Spearman correlation coefficient will be computed depending on the distribution.
- Bland-Altman and correlation plots will be performed.

These errors will be compared to the inter-observer variabilities assessed in the study (see section 5.5.2) and the inter-observer variabilities assessed in the literature.

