ANALYSIS	
Patient description: The population will be described in terms of demographics, ultrasound parameters, and pathology.
 
Endpoints: For all quality criteria, the percentage of success and its confidence interval will be evaluated for acquisitions performed by experts and acquisitions performed by novices. This analysis will be performed via a multi-reader, multi-case power analysis.
 
For each qualitative ultrasound measurement, taking into account the experts' acquisition as the reference, the following parameters will be evaluated:
 
 
● Percentage of agreement
 
● Sensitivity
 
● Specificity
 
● Precision
 
● Recall
 
● F1-score
 
● Area under the curve
 
 
For each quantitative ultrasound measurement:
 
 
● The mean, standard deviation and 95% confidence interval of the difference will be calculated between the measurements made on the acquisitions obtained by the experts and those obtained by the novices
 
● Bland-Altman plots and correlation plots will be performed.
 
 
Sensitivity studies will be performed on the investigating centers, prior cardiac diagnoses, and obese patients.

DESKi	PROSPECTIVE EVALUATION OF HEARTFOCUS: A SOFTWARE SUPPORTING THE ACQUISITION OF CARDIAC ULTRASOUND EXAMS	HF-01 Version:4.2
-------	---------------------------------------------------------------------------------------------------------	----------------------

	The evaluation of HeartEF will be performed by comparing the results from the algorithm to the manual cardiologist's analysis.
--	--------------------------------------------------------------------------------------------------------------------------------

EXPECTED IMPACTS	
From a medical point of view, there will be no direct benefit for the patient included in the analysis.
 
At a larger scale, HeartFocus software will outlook access to ultrasound exams by allowing non-experts (emergency physicians, residents, general practitioners, paramedics, and nurses) to acquire cardiac ultrasound exams of sufficient quality for their analysis, without any previous experience in echography.
 
This would improve patient management by optimizing the care pathway, with echography being used as a screening or follow-up tool for patients.

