2.1 Study Design

This prospective multicentric international non-inferiority pivotal investigation will evaluate the ability of the Heartfocus software to support novices for the acquisition of 10 reference views of cardiac ultrasound. The 10 reference views are the following:

- apical 2-chamber (A2C),
- apical 3-chamber (A3C),
- apical 4-chamber (A4C),
- apical 5-chamber (A5C),
- parasternal long axis (PLAX),
- parasternal short axis at the aortic valve (PSAX-AV),
- parasternal short axis at the mitral valve (PSAX-MV),
- parasternal short axis at the papillary muscles (PSAX-PM),
- subcostal 4-chamber (SC-4C),
- subcostal inferior vena cava (SC-IVC).

Novices will be nurses without prior ultrasound experience who have received dedicated training on cardiac ultrasound and Heartfocus software.

Patients included in the study will be adult patients scheduled for an echocardiogram at one of the two investigating centers. Each patient included in the study will receive a standard cardiac ultrasound exam performed in the standard way with the regular ultrasound system used in the cardiologic service.

Patients will receive 2 additional limited exams to their standard exam, which consist of the acquisition of ultrasound clips for each of the 10 reference views:

- one by a novice, *i.e.* nurses having received a dedicated training of 2 days, with the Clarius phased array probe and the HeartFocus software with the guidance system,
- one by an expert (experienced sonographer cardiologist) with the Clarius phased array probe and the HeartFocus software without the guidance system.

A total of 8 novices will perform the acquisition on 30 different patients each. In total 240 patients will be included in the analysis, half in each investigator center. The exams (240 acquired by novices, 240 by experts) will be assessed by an independent review committee, composed of 5 different cardiologists. Each exam will be reviewed by all 5 cardiologists from this committee. Cardiologists will not know if the exam was performed by a novice or an expert. Cardiologists will be blinded to the investigating center in which the acquisition has been performed.

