2.2 Collected Data

The following data will be collected for both the exam acquired by the expert and the exam acquired by the novice:

- Whether the exam was acquired by the expert/novice,
- Reason for not acquiring the exam,
- Whether the exam has successfully been exported for review by the cardiologists,
- Number of clips acquired by the expert/novice,
- Novice acquisition duration in minutes,
- Report of Adverse event (AE) with details, start and end date, severity, relationship, action taken and outcome,
- Report of Device deficiency (DD) with details, date, type, and reason of deficiency, action taken and outcome,
- Report of Serious adverse event (SAE) with details, start and end date, severity, relationship, action taken, and outcome.

The following data will be collected for each review performed by each cardiologist on each exam for qualitative assessment:

- Qualitative assessments
- For the 10 reference views of cardiac ultrasound (PLAX, PSAX-PM, PSAX-MV, PSAX-AV, A4C, A5C, A2C, A3C, SC-4C and SC-IVC), quality of diagnostic (Yes/No/No clip),
- Qualitative visual assessment of left ventricular size (Yes/No) and type* (if Yes),
- Qualitative visual assessment of left ventricular function (Yes/No) and type* (if Yes),
- Qualitative visual assessment of right ventricular size (Yes/No) and type* (if Yes),
- Qualitative visual assessment of right ventricular function (Yes/No) and type* (if Yes),
- Qualitative visual assessment of non-trivial pericardial effusion (Yes/No) and type* (if Yes),
- Qualitative visual assessment of left atrial size (Yes/No) and type* (if Yes),
- Qualitative visual assessment of right atrial size (Yes/No) and type* (if Yes),
- Qualitative visual assessment of segmental kinetics of the left ventricle (Yes/No) and type* (if Yes),
- Qualitative visual assessment of aortic valve (Yes/No) and type* (if Yes),
- Qualitative visual assessment of mitral valve (Yes/No) and type* (if Yes),
- Qualitative visual assessment of tricuspid valve (Yes/No) and type* (if Yes),
- Qualitative visual assessment of inferior vena cava size (Yes/No) and type* (if Yes).

* For each assessment, the type will be described in section 3.4.1.

The following data will be collected for each review performed by each cardiologist on each exam for quantitative assessment:

- For PLAX clip:
 - If measurement = Yes, IVSd, LVEDD, and PWd measurement (in mm),
 - If measurement = Yes, LVESD measurement (in mm),

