 - If measurement = Yes, Aortic root measurement (in mm),
- For A4C clip:
 - If measurement = Yes, A4C single-plane LV EDV and LV ESV measurement (in mL) and LV EF measurement (in %),
- For A2C clip:
 - If measurement = Yes, A2C single-plane LV EDV and LV ESV measurement (in mL), LV EF measurement (in %),
- For A4C and A2C clips:
 - If measurement = Yes, Biplane LV EDV and LV ESV measurement (in mL) and Biplane LV EF measurement (in %),
- For SC-IVC clip:
 - If measurement = Yes, Diameter of the IVC measurement (in mm).

The following data will be collected for each patient:

- Information regarding consent form and eligibility criteria,
- Information regarding premature discontinuation (date of end of study and reason for study exit),
- Demographics (age, sex, height, weight, BMI, ethnicity*, race*),
- Indication for cardiac ultrasound exam,
- Prior cardiac diagnoses (hypertension, hyperlipidemia, diabetes, heart failure, atrial fibrillation, other arrhythmias, coronary artery disease, prior heart attack, valvular heart disease, pulmonary hypertension, heart transplant, cardiomyopathies, congenital heart disease, other and specification of other prior cardiac diagnoses, none, not reported),
- Prior non-cardiac diagnoses (renal disease, COPD/emphysema, pulmonary embolus, systemic infiltrative disease like amyloid or hemochromatosis, cancer, underwent chemotherapy, underwent radiation, other and specification of other prior non-cardiac diagnoses, none, not reported),
- Implanted medical devices (pacemaker/ICD, leadless pacemaker, prosthetic heart valve, LAA closure device, atrial septal defect closure device, ventricular septal defect closure device, patent foramen ovale closure device, valve repair device, other and specification of other implanted medical devices, none, not reported),
- Cardiac abnormalities (abnormal left ventricular size or function, abnormal right ventricular size or function, abnormal left atrial size, abnormal right atrial size, septal defect, abnormal mitral valve, abnormal tricuspid valve, abnormal aortic valve, non-trivial pericardial effusion, abnormal inferior vena cava size, patent foramen ovale, other and specification of other cardiac abnormalities, none, not reported).

* Only collected for US patients.

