5.5.2 Inter-Observer Study

The purpose of the inter-observer study is to check the reproducibility of a review by different cardiologists. The inter-observer study will be performed twice, in the FAS population:

- on novices' exams,
- on experts' exams.

For each qualitative (primary, quality, and clinical qualitative) endpoint:

- The number and proportion of exams where at least 3, 4, and 5 cardiologists agree will be computed.
- The agreement between each pair of cardiologists will be assessed using the agreement rate, and its 95% CI.

For each quantitative (clinical quantitative) endpoint:

- The mean, standard deviation, and 95% CI of the difference between the assessments of each pair of cardiologists will be calculated.
- The concordance of measurements will be assessed using the ICC, and its 95% CI.

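### SAP 5.5.3 compares HeartEF's error against an average of 3 to 5 cardiologists with the variability between single cardiologists, so the SDs and ICCs are not like for like

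*SAP*

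**What the plan says.** Evaluating HeartEF is a secondary objective (SAP 3.2). SAP 5.5.3 reports the mean, SD and 95% CI of "the difference between the left ventricle assessment with HeartEF and the average of the assessments made by at least 3 cardiologists", with an ICC, a correlation coefficient and Bland-Altman plots.

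The benchmark comes from SAP 5.5.2, which for quantitative endpoints states: "The mean, standard deviation, and 95% CI of the difference between the assessments of each pair of cardiologists will be calculated". An ICC is reported there as well.

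Section 5.5.3 links the two: "These errors will be compared to the inter-observer variabilities assessed in the study (see section 5.5.2". The same sentence adds variability from the literature as a second benchmark, without defining it. It does not say which statistic is compared, gives no rescaling and sets no limit. Neither section plans a comparison of HeartEF with a single cardiologist.

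The single-reader data will exist. SAP 2.1 says: "Each exam will be reviewed by all 5 cardiologists from this committee". SAP 2.2 introduces the quantitative data with "The following data will be collected for each review performed by each cardiologist on each exam for quantitative assessment", and the list includes biplane volumes and EF.

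**The concern.** One side of the comparison is an algorithm minus a mean of three to five readers. The other is one reader minus one reader. The mean carries less reader noise than a single reading, so the HeartEF SD shrinks for a reason unrelated to HeartEF, while the benchmark keeps the full noise of two readers.

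This is the only in-study yardstick for HeartEF error. With no acceptance limit, a statement that HeartEF lies within inter-observer variability would carry the interpretation, in a trial that the protocol says is meant to supply evidence for FDA and CE certification. An algorithm that agrees with cardiologists less well than they agree with each other could earn that statement.

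**Working it through.** **Inputs.** The number of readers averaged, k, is at least 3 (SAP 5.5.3) and at most 5 (SAP 2.1). Sections 5.5.2 and 5.5.3 give no SD, margin or sample size, so there is no plan figure to reproduce. Reader-error figures below are assumptions.

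**Step 1: agreement with readers, no error model needed.** When the same k readers measure the same exams, this is an algebraic identity:

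Var(HeartEF − mean of k) = average Var(HeartEF − one reader) − [(k−1)/(2k)] × average Var(reader pair).

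Dividing by the average pair variance gives

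(planned ratio)² = (single-reader ratio)² − (k−1)/(2k).

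The deduction is 1/3 for k=3, 0.375 for k=4 and 0.40 for k=5, whatever error the readers share. If HeartEF agrees with each reader as they agree with each other, the single-reader ratio is 1 and the planned ratio is:

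- k=3: √(1 − 0.333) = 0.816
- k=4: √(1 − 0.375) = 0.791
- k=5: √(1 − 0.40) = 0.775

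HeartEF therefore looks 18% to 23% tighter with no real advantage. Conversely, the planned ratio reaches 1 only when the single-reader ratio is √1.333 = 1.155 (k=3) or √1.40 = 1.183 (k=5). HeartEF can disagree with single cardiologists 15% to 18% more than they disagree with each other and still look equal.

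**Step 2: ICC.** Assume independent errors, HeartEF as precise as one reader (error variance 1) and a between-exam SD of 2 reader-error SDs (variance 4). A reader pair gives 4/(4+1) = 0.80. For HeartEF against the mean, the average error variance is (1+1/k)/2, which is 0.667 (k=3) or 0.60 (k=5). The ICC is 4/4.667 = 0.86 or 4/4.60 = 0.87.

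**Step 3: error against the true value.** Let rho be the share of reader error variance common to all readers, and g the covariance of HeartEF error with reader error. Set HeartEF's total error variance equal to one reader's, at 1. Then:

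- Var(HeartEF − mean of k) = 1 + rho + (1−rho)/k − 2g
- Var(reader pair) = 2(1−rho)
- Var(HeartEF − one reader) = 2 − 2g

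SD ratios to the reader pair:

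| HeartEF shares | rho | Planned, k=3 / k=5 | Single-reader |
|---|---|---|---|
| all of the common error (g=rho) | any | 0.816 / 0.775 | 1.000 |
| half (g=rho/2) | 0.1 | 0.850 / 0.810 | 1.027 |
| half | 0.2 | 0.890 / 0.851 | 1.061 |
| half | 0.3 | 0.939 / 0.902 | 1.102 |
| none (g=0) | 0.1 | 0.882 / 0.843 | 1.054 |
| none | 0.2 | 0.957 / 0.922 | 1.118 |
| none | 0.3 | 1.047 / 1.014 | 1.195 |

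The planned ratio passes 1 above rho = 0.25 (k=3) or 0.286 (k=5) if HeartEF shares none, and above 0.40 or 0.444 if it shares half. The table agrees with Step 1: for g=0, rho=0.2 and k=3, 1.118² − 1/3 = 0.917, whose root is 0.957.

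**Step 4: sampling noise.** Simulated 95% ranges of the planned ratio, with normal errors and HeartEF sharing all common error (or none existing):

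| Comparison | 240 measured exams | 120 measured exams |
|---|---|---|
| Ten pairs pooled, k=3 | 0.74–0.90 | 0.70–0.94 |
| Ten pairs pooled, k=5 | 0.70–0.86 | 0.67–0.89 |
| One pair, k=3, readers missing at random | 0.68–1.00 | 0.63–1.08 |

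Pooled, the artefact stands clear of noise. For one pair at k=3, where fewer exams have both readings, it may not.

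**The case against.** **The statistic is not named.** Section 5.5.3 speaks only of errors, so a comparison of SDs is an inference. That stands. SD and ICC are the natural reading because both sections list them, and the mismatch affects both. It does not affect the mean difference, because averaging the reference does not shrink a systematic bias.

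**The direction is not fixed.** A reader might infer that the plan always flatters HeartEF. The documents do not support that for error against truth: they give no reader-error figures, and Step 3 shows the ratio can exceed 1 when readers share error that HeartEF does not. What holds without a model is narrower. As a measure of agreement with readers, the planned ratio is always below the like-for-like ratio. Reader values are the only reference planned for HeartEF, so agreement is what this benchmark can address.

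**The single-reader comparison is not neutral either.** If HeartEF shares none of the common error, it looks 5% to 20% worse than readers for rho from 0.1 to 0.3. The planned ratio is then nearer 1 above rho of about 0.15 (k=3) or 0.17 (k=5). This stands as a reason to state the limitation and to keep the comparison with the reader mean as a description.

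**Different exam sets.** A reader might add that 5.5.2 and 5.5.3 use different exams, since 5.5.3 depends on the "exams on which HeartEF was able to make the quantitative assessment" and on at least 3 cardiologist values. Both sections use the FAS, and nothing shows how far the measured sets differ. The point carries no weight here beyond using common exams in the fix.

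**Low consequence.** HeartEF sits under the SAP's other analyses with no test or success rule, and the plan still reports bias, SD and Bland-Altman plots. This limits the severity but does not make the two quantities comparable.

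**Conclusion.** The concern holds. Followed as written, SAP 5.5.3 sets unlike quantities side by side. A HeartEF interchangeable with a cardiologist would show an SD ratio of 0.82 (k=3) to 0.77 (k=5) instead of 1. Those figures follow from the identity, given the same k readers on the same exams. The ICC inflation, about 0.86 to 0.87 against 0.80, rests on the assumed between-exam spread, independent errors and equal precision.

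The documents do not support the further inference that HeartEF's accuracy will be overstated. Against truth, the direction depends on the error that HeartEF shares with the readers. Nor would the artefact be visible in every pair: it exceeds sampling noise with pooled pairs or with k=5, but perhaps not for a single pair at k=3.

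The effect is confined to the interpretation of one descriptive comparison for a secondary objective. It should be corrected before the analysis. The primary endpoints are untouched.

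**What to change.** In SAP 5.5.3:

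- Name the statistics compared: SD or limits of agreement, and ICC.
- For the in-study benchmark, compute HeartEF minus each individual cardiologist for biplane ESV, EDV and EF (5 comparisons). Set the SD, limits of agreement and ICC beside those of the 10 cardiologist pairs. Use the same exams on both sides, separately for novices' and experts' exams.
- Keep HeartEF versus the reader mean as the accuracy description, but do not set its SD or ICC against the pair values.
- Apply the same rule to the literature benchmark wherever the published figure is for pairs of single readers.
- State in the report that error shared only by the readers counts against HeartEF in the single-reader comparison.

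The cost is SAP wording and a little more analysis. No new data are needed, since biplane values are collected per cardiologist (SAP 2.2). The protocol's Analysis section accommodates the change: "The evaluation of HeartEF will be performed by comparing the results from the algorithm to the manual" reading by the cardiologist, without specifying one reader or an average. The downside is that HeartEF may look less favourable.

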5.5.4 Comparison to Competitors

The performance of HeartFocus software will be compared to the ones of our competitors. The purpose of this analysis is to check whether our results are similar to theirs.

This comparison will be performed in the clinical report. It will summarize and explain the results, taking into account the results of the different studies.

5.6 Safety Analyses

All safety analyses will be performed using the safety analysis set.

A listing will be provided for

- all adverse events,
- all device deficiencies,
- all serious adverse events.

A separate listing will be provided for

- events leading to study discontinuation,
- events leading to death.

5.6.1 Adverse Events

Adverse events will be summarized in terms (number and proportion) of

- expectation,
- severity,
- relationship to the exam,
- taken action,
- outcome.

Among these AEs, the number and proportion of AEs due to DDs will be computed. In addition, the number and proportion of SAEs among these AEs will be computed.

5.6.2 Device Deficiencies

Device deficiencies will be summarized (number and proportion) in terms of causes and taken actions. In addition, the number and proportion of DDs that lead to SAEs will be computed.

5.6.3 Serious Adverse Events

Serious adverse events will be summarized in terms (number and proportion) of

- expectation,
- severity,
- relationship to the procedure,
- relationship to the device,
- taken action,
- outcome.

5.7 Sequence of Planned Analyses

The analyses will be performed when all patients of both the French and the USA sites have their ultrasound exams (performed by novices, experts, or both), the latter being reviewed by all 5 cardiologists.
